**SITE REACTIONS TO INJECTIONS AND INFUSIONS**

Parameter	Grade 1 Mild	Grade 2 Moderate	Grade 3 Severe	Grade 4 Potentially life-threatening
Injection Site Pain or Tenderness Report only one	Pain or tenderness causing no or minimal limitation of use of limb	Pain or tenderness causing greater than minimal limitation of use of limb	Pain or tenderness causing inability to perform usual social & functional activities	Pain or tenderness causing inability to perform basic self-care function OR Hospitalization indicated
Injection Site Erythema or Redness  Report only one > 15 years of age	2.5 to < 5 cm in diameter OR 6.25 to < 25 cm  surface area AND Symptoms causing no or minimal interference with usual social & functional activities	≥ 5 to < 10 cm in diameter OR ≥ 25 to < 100 cm  surface area OR Symptoms causing greater than minimal interference with usual social & functional activities	≥ 10 cm in diameter OR ≥ 100 cm  surface area OR Ulceration OR Secondary infection OR Phlebitis OR Sterile abscess OR Drainage OR Symptoms causing inability to perform usual social & functional activities	Potentially life-threatening consequences (e.g., abscess, exfoliative dermatitis, necrosis involving dermis or deeper tissue)
Injection Site Induration or Swelling Report only one > 15 years of age	Same as for Injection Site Erythema or Redness, > 15 years of age	Same as for Injection Site Erythema or Redness, > 15 years of age	Same as for Injection Site Erythema or Redness, > 15 years of age	Same as for Injection Site Erythema or Redness, > 15 years of age
Injection Site Pruritus	Itching localized to the injection site that is relieved spontaneously or in < 48 hours of treatment	Itching beyond the injection site that is not generalized OR Itching localized to the injection site requiring ≥ 48 hours treatment	Generalized itching causing inability to perform usual social & functional activities	NA

12 Injection Site Erythema or Redness should be evaluated and graded using the greatest single diameter or measured surface area.

**LABORATORY VALUES\* CHEMISTRIES**

Parameter	Grade 1 Mild	Grade 2 Moderate	Grade 3 Severe	Grade 4 Potentially life-threatening
Acidosis	NA	pH $\geq$ 7.3 to < LLN	pH < 7.3 without life-threatening consequences	pH < 7.3 with life-threatening consequences
Albumin, Low (g/dL; g/L)	3.0 to < LLN 30 to < LLN	$\geq$ 2.0 to < 3.0 $\geq$ 20 to < 30	< 2.0 < 20	NA
Alkaline Phosphatase, High	1.25 to < 2.5 x ULN	2.5 to < 5.0 x ULN	5.0 to < 10.0 x ULN	$\geq$ 10.0 x ULN
Alkalosis	NA	pH > ULN to $\leq$ 7.5	pH > 7.5 without life-threatening consequences	pH > 7.5 with life-threatening consequences
ALT or SGPT, High Report only one	1.25 to < 2.5 x ULN	2.5 to < 5.0 x ULN	5.0 to < 10.0 x ULN	$\geq$ 10.0 x ULN
Amylase (Pancreatic) or Amylase (Total), High Report only one	1.1 to < 1.5 x ULN	1.5 to < 3.0 x ULN	3.0 to < 5.0 x ULN	$\geq$ 5.0 x ULN
AST or SGOT, High Report only one	1.25 to < 2.5 x ULN	2.5 to < 5.0 x ULN	5.0 to < 10.0 x ULN	$\geq$ 10.0 x ULN
Bicarbonate, Low (mEq/L; mmol/L)	16.0 to < LLN 16.0 to < LLN	11.0 to < 16.0 11.0 to < 16.0	8.0 to < 11.0 8.0 to < 11.0	< 8.0 < 8.0
Bilirubin Direct Bilirubin  , High > 28 days of age	NA	NA	> ULN with other signs and symptoms of hepatotoxicity	> ULN with life-threatening consequences (e.g., signs and symptoms of liver failure)
Total Bilirubin, High > 28 days of age	1.1 to < 1.6 x ULN	1.6 to < 2.6 x ULN	2.6 to < 5.0 x ULN	$\geq$ 5.0 x ULN
Calcium, High (mg/dL; mmol/L) $\geq$ 7 days of age	10.6 to < 11.5 2.65 to < 2.88	11.5 to < 12.5 2.88 to < 3.13	12.5 to < 13.5 3.13 to < 3.38	$\geq$ 13.5 $\geq$ 3.38
Calcium (Ionized), High (mg/dL; mmol/L)	> ULN to < 6.0 > ULN to < 1.5	6.0 to < 6.4 1.5 to < 1.6	6.4 to < 7.2 1.6 to < 1.8	$\geq$ 7.2 $\geq$ 1.8
Calcium, Low (mg/dL; mmol/L) $\geq$ 7 days of age	7.8 to < 8.4 1.95 to < 2.10	7.0 to < 7.8 1.75 to < 1.95	6.1 to < 7.0 1.53 to < 1.75	< 6.1 < 1.53
Calcium (Ionized), Low (mg/dL; mmol/L)	< LLN to 4.0 < LLN to 1.0	3.6 to < 4.0 0.9 to < 1.0	3.2 to < 3.6 0.8 to < 0.9	< 3.2 < 0.8

Parameter	Grade 1 Mild	Grade 2 Moderate	Grade 3 Severe	Grade 4 Potentially life-threatening
Cardiac Troponin I, High	NA	NA	NA	Levels consistent with myocardial infarction or unstable angina as defined by the local laboratory
Creatine Kinase, High	3 to < 6 x ULN	6 to < 10x ULN	10 to < 20 x ULN	≥ 20 x ULN
Creatinine, High **Report only one	1.1 to 1.3 x ULN	> 1.3 to 1.8 x ULN OR Increase to 1.3 to < 1.5 x participant's baseline	> 1.8 to < 3.5 x ULN OR Increase to 1.5 to < 2.0 x participant's baseline	≥ 3.5 x ULN OR Increase of ≥ 2.0 x participant's baseline
Creatinine Clearance  or eGFR, Low **Report only one	NA	< 90 to 60 ml/min or ml/min/1.73 m  OR 10 to < 30% decrease from participant's baseline	< 60 to 30 ml/min or ml/min/1.73 m  OR 30 to < 50% decrease from participant's baseline	< 30 ml/min or ml/min/1.73 m  OR ≥ 50% decrease from participant's baseline or dialysis needed
Glucose (mg/dL; mmol/L) Fasting, High Nonfasting, High	110 to 125 6.11 to < 6.95  116 to 160 6.44 to < 8.89	> 125 to 250 6.95 to < 13.89  > 160 to 250 8.89 to < 13.89	> 250 to 500 13.89 to < 27.75  > 250 to 500 13.89 to < 27.75	≥ 500 ≥ 27.75  ≥ 500 ≥ 27.75
Glucose, Low (mg/dL; mmol/L) ≥ 1 month of age	55 to 64 3.05 to <3.55	40 to < 55 2.22 to < 3.05	30 to < 40 1.67 to < 2.22	< 30 < 1.67
Lactate, High	ULN to < 2.0 x ULN without acidosis	≥ 2.0 x ULN without acidosis	Increased lactate with pH < 7.3 without life-threatening consequences	Increased lactate with pH < 7.3 with life-threatening consequences
Lipase, High	1.1 to < 1.5 x ULN	1.5 to < 3.0 x ULN	3.0 to < 5.0 x ULN	≥ 5.0 x ULN
Lipid Disorders (mg/dL; mmol/L) Cholesterol, Fasting, High ≥ 18 years of age	200 to < 240 5.18 to < 6.19	240 to < 300 6.19 to < 7.77	≥ 300 ≥ 7.77	NA
LDL, Fasting, High ≥ 18 years of age	130 to < 160 3.37 to < 4.12	160 to < 190 4.12 to < 4.90	≥ 190 ≥ 4.90	NA
Triglycerides, Fasting, High	150 to 300 1.71 to 3.42	>300 to 500 >3.42 to 5.7	>500 to < 1,000 >5.7 to 11.4	> 1,000 > 11.4
Magnesium  , Low (mEq/L; mmol/L)	1.2 to < 1.4 0.60 to < 0.70	0.9 to < 1.2 0.45 to < 0.60	0.6 to < 0.9 0.30 to < 0.45	< 0.6 < 0.30

Parameter	Grade 1 Mild	Grade 2 Moderate	Grade 3 Severe	Grade 4 Potentially life-threatening
Phosphate, Low (mg/dL; mmol/L) > 14 years of age	2.0 to < LLN 0.65 to < LLN	1.4 to < 2.0 0.45 to < 0.65	1.0 to < 1.4 0.32 to < 0.45	< 1.0 < 0.32
Potassium, High (mEq/L; mmol/L)	5.6 to < 6.0 5.6 to < 6.0	6.0 to < 6.5 6.0 to < 6.5	6.5 to < 7.0 6.5 to < 7.0	≥ 7.0 ≥ 7.0
Potassium, Low (mEq/L; mmol/L)	3.0 to < 3.4 3.0 to < 3.4	2.5 to < 3.0 2.5 to < 3.0	2.0 to < 2.5 2.0 to < 2.5	< 2.0 < 2.0
Sodium, High (mEq/L; mmol/L)	146 to < 150 146 to < 150	150 to < 154 150 to < 154	154 to < 160 154 to < 160	≥ 160 ≥ 160
Sodium, Low (mEq/L; mmol/L)	130 to < 135 130 to < 135	125 to < 130 125 to < 130	121 to < 125 121 to < 125	≤ 120 ≤ 120
Uric Acid, High (mg/dL; mmol/L)	7.5 to < 10.0 0.45 to < 0.59	10.0 to < 12.0 0.59 to < 0.71	12.0 to < 15.0 0.71 to < 0.89	≥ 15.0 ≥ 0.89
HEMATOLOGY				
Absolute CD4+ Count, Low (cell/mm  ; cells/L) > 5 years of age (not HIV infected)	300 to < 400 300 to < 400	200 to < 300 200 to < 300	100 to < 200 100 to < 200	< 100 < 100
Absolute Lymphocyte Count, Low (cell/mm  ; cells/L) > 5 years of age (not HIV infected)	600 to < 650 0.600 x 10  to < 0.650 x 10 	500 to < 600 0.500 x 10  to < 0.600 x 10 	350 to < 500 0.350 x 10  to < 0.500 x 10 	< 350 < 0.350 x 10 
Absolute Neutrophil Count (ANC), Low (cells/mm  ; cells/L) > 7 days of age	800 to 1,000 0.800 x 10  to 1.000 x 10 	600 to 799 0.600 x 10  to 0.799 x 10 	400 to 599 0.400 x 10  to 0.599 x 10 	< 400 < 0.400 x 10 
Fibrinogen, Decreased (mg/dL; g/L)	100 to < 200 1.00 to < 2.00 OR 0.75 to < 1.00 x LLN	75 to < 100 0.75 to < 1.00 OR ≥ 0.50 to < 0.75 x LLN	50 to < 75 0.50 to < 0.75 OR 0.25 to < 0.50 x LLN	< 50 < 0.50 OR < 0.25 x LLN OR Associated with gross bleeding
Hemoglobin  , Low (g/dL; mmol/L)  ≥ 13 years of age (male only)	10.0 to 10.9 6.19 to 6.76	9.0 to < 10.0 5.57 to < 6.19	7.0 to < 9.0 4.34 to < 5.57	< 7.0 < 4.34
≥ 13 years of age (female only)	9.5 to 10.4 5.88 to 6.48	8.5 to < 9.5 5.25 to < 5.88	6.5 to < 8.5 4.03 to < 5.25	< 6.5 < 4.03
INR, High (not on anticoagulation therapy)	1.1 to < 1.5 x ULN	1.5 to < 2.0 x ULN	2.0 to < 3.0 x ULN	≥ 3.0 x ULN
Methemoglobin (% hemoglobin)	5.0 to < 10.0%	10.0 to < 15.0%	15.0 to < 20.0%	≥ 20.0%

Parameter	Grade 1 Mild	Grade 2 Moderate	Grade 3 Severe	Grade 4 Potentially life-threatening
PTT, High (not on anticoagulation therapy)	1.1 to < 1.66 x ULN	1.66 to < 2.33 x ULN	2.33 to < 3.00 x ULN	≥ 3.00 x ULN
Platelets, Decreased (cells/mm  ; cells/L)	100,000 to < 125,000 100,000 x 10  to < 125,000 x 10 	50,000 to < 100,000 50,000 x 10  to < 100,000 x 10 	25,000 to < 50,000 25,000 x 10  to < 50,000 x 10 	< 25,000 < 25,000 x 10 
PT, High (not on anticoagulation therapy)	1.1 to < 1.25 x ULN	1.25 to < 1.50 x ULN	1.50 to < 3.00 x ULN	≥ 3.00 x ULN
WBC, Decreased (cells/mm  ; cells/L) > 7 days of age	2,000 to 2,499 2,000 x 10  to 2,499 x 10 	1,500 to 1,999 1,500 x 10  to 1,999 x 10 	1,000 to 1,499 1,000 x 10  to 1,499 x 10 	< 1,000 < 1,000 x 10 
URINALYSIS				
Glycosuria (random collection tested by dipstick)	Trace to 1+ or ≤ 250 mg	2+ or > 250 to ≤ 500 mg	> 2+ or > 500 mg	NA
Hematuria (not to be reported based on dipstick findings or on blood believed to be of menstrual origin)	6 to < 10 RBCs per high power field	≥ 10 RBCs per high power field	Gross, with or without clots OR With RBC casts OR Intervention indicated	Life-threatening consequences
Proteinuria (random collection tested by dipstick)	1+	2+	3+ or higher	NA

\* Reminder: An asymptomatic abnormal laboratory finding without an accompanying AE should not be reported to DAIDS in an expedited time frame unless it meets protocol-specific reporting requirements.

13 Direct bilirubin >1.5 mg/dL in a participant <28 days of age should be graded as grade 2, if <10% of the total bilirubin.

\*\* Reminder: Choose the method that selects for the higher grade.

14 Use the applicable formula (ie, Cockcroft-Gault in mL/min or Schwartz, MDRD, CKD-Epi in mL/min/1.73m^2). Sites should choose the method defined in their study and when not specified, use the method most relevant to the study population.

15 To convert a magnesium value from mg/dL to mmol/L, laboratories should multiply by 0.4114.

16 Male and female sex are defined as sex at birth. For transgender participants ≥13 years of age who have been on hormone therapy for more than 6 consecutive months, grade hemoglobin based on the gender with which they identify (ie, a transgender female should be graded using the female sex at birth hemoglobin laboratory values).

17 The most commonly used conversion factor to convert g/dL to mmol/L is 0.6206. For grading hemoglobin results obtained by an analytic method with a conversion factor other than 0.6206, the result must be converted to g/dL using appropriate conversion factor for the particular laboratory.

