## **7.2. Laboratory Evaluations**

### **7.2.1. Graded Laboratory Values**

The criteria specified in the study protocol will be used to grade laboratory results as normal (no grade), mild (Grade 1), moderate (Grade 2), severe (Grade 3) or potentially life threatening (Grade 4). See Appendix 1 of the protocol for detailed DAIDS grading criteria on the relevant laboratory tests. For laboratory tests with criteria for both increased and decreased levels, analyses for each direction (ie, increased, decreased) will be presented separately.

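### In Appendix 1 the cells/L grade limits for platelets and WBC are 1000 times the cells/mm³ limits beside them, and the SAP does not say which unit is graded

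*Combined protocol and SAP*

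**What the plan says.** The platelet and WBC rows of Protocol Appendix 1 (Hematology) are each labelled with two units, cells/mm³ and cells/L, and each grade cell gives one set of limits per unit. In the quotes below, the superscript 9 follows the final 10.

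- Platelets, Grade 1: "100,000 to < 125,000 100,000 x 10"; Grade 3: "25,000 to < 50,000 25,000 x 10"; Grade 4: "< 25,000 < 25,000 x 10".
- WBC, Grade 1: "2,000 to 2,499 2,000 x 10"; Grade 4: "< 1,000 < 1,000 x 10".
- Absolute neutrophil count (ANC), Grade 1, same block and units: "800 to 1,000 0.800 x 10".
- Absolute lymphocyte count, Grade 1, same block and units: "600 to < 650 0.600 x 10".

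The table is used in the analysis. Abnormal laboratory results are a component of the primary endpoint (Protocol 3.2.1). Protocol 10.4.5.2 grades laboratory values by Appendix 1, and SAP 7.2.1 directs the reader to it: "See Appendix 1 of the protocol for detailed DAIDS grading criteria on the relevant laboratory tests". SAP 7.2.1.1 calls an abnormality treatment-emergent when it is at least one grade worse than Baseline. Protocol 8.8.4 sends the tests to central laboratories without giving a reporting unit.

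**The concern.** The two limits within one platelet or WBC cell should describe the same count, but they differ by a factor of 1000. A program that takes the cells/mm³ line and one that takes the cells/L line would grade the same sample differently, and nothing in the SAP says which line to take.

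The part of the primary endpoint that rests on graded platelet and WBC results is at stake. The treatment-emergent rule makes the failure awkward. If Baseline is already at the highest grade, no later value can be worse, so a real fall in platelets or WBC would leave no trace in that table. A zero row looks like reassurance rather than an error.

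**Working it through.** **Inputs.** All limits are from Protocol Appendix 1, Hematology. The treatment-emergent rule is from SAP 7.2.1.1. The platelet exclusion limit (below 100,000/mm³) is from Protocol 5.3, criterion 11a.

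**Conversion.** 1 mm³ = 10⁻⁶ L, so 1 cell/mm³ = 10⁶ cells/L, and the limit in 10⁹/L = (limit in cells/mm³) / 1000.

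**Step 1: rows that should reproduce.** ANC: 800/1000 = 0.800, printed 0.800; 1,000/1000 = 1.000, printed 1.000. Lymphocytes: 600/1000 = 0.600, printed 0.600; 650/1000 = 0.650, printed 0.650. The remaining limits in these two rows also agree (ratio 1.0). The table's own convention is therefore a true conversion with a decimal point.

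**Step 2: platelets and WBC.**

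| Row, limit | cells/mm³ | Converted (10⁹/L) | Printed (10⁹/L) | Ratio |
|---|---|---|---|---|
| Platelets, Grade 1 upper | 125,000 | 125 | 125,000 | 1000 |
| Platelets, Grade 1 lower | 100,000 | 100 | 100,000 | 1000 |
| Platelets, Grade 2 lower | 50,000 | 50 | 50,000 | 1000 |
| Platelets, Grade 3 lower / Grade 4 | 25,000 | 25 | 25,000 | 1000 |
| WBC, Grade 1 upper | 2,499 | 2.499 | 2,499 | 1000 |
| WBC, Grade 1 lower | 2,000 | 2.000 | 2,000 | 1000 |
| WBC, Grade 2 upper | 1,999 | 1.999 | 1,999 | 1000 |
| WBC, Grade 2 lower | 1,500 | 1.500 | 1,500 | 1000 |
| WBC, Grade 3 upper | 1,499 | 1.499 | 1,499 | 1000 |
| WBC, Grade 3 lower / Grade 4 | 1,000 | 1.000 | 1,000 | 1000 |

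Each row prints two limits for each of Grades 1 to 3 and one for Grade 4, so 7 per row and 14 in the 8 cells. All carry the factor 1000.

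**Step 3: grades that each line would give.**

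| Result (10⁹/L) | Grade on printed cells/L line | Grade on cells/mm³ line or its conversion |
|---|---|---|
| Platelets 60 | 4 | 2 |
| Platelets 100 | 4 | 1 |
| Platelets 250 | 4 | none |
| Platelets 1000 | 4 | none |
| WBC 1.2 | 4 | 3 |
| WBC 2.2 | 4 | 1 |
| WBC 7 | 4 | none |
| WBC 50 | 4 | none |

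To escape Grade 4 on the printed cells/L line, a subject would need 25,000 × 10⁹ / 10⁶ = 25,000,000 platelets/mm³, or 1,000 × 10⁹ / 10⁶ = 1,000,000 WBC/mm³. A subject exactly at the platelet eligibility limit (100,000/mm³) is Grade 1 on one line and Grade 4 on the other.

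**Step 4: effect on the treatment-emergent rule.** If the printed cells/L line were programmed, Baseline would be Grade 4 and the largest possible increase would be 4 − 4 = 0, below the one grade required. No subject with a Baseline value could have a treatment-emergent platelet or WBC decrease. A subject with a missing Baseline would be counted as a Grade 4 event whatever the count, because SAP 7.2.1.1 counts any graded value in that case.

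**The case against.** The strongest reply is that this may be one misread character. If the commas in the cells/L entries are decimal points, every entry is exactly right and matches the three-decimal format of the ANC and lymphocyte rows (100.000, 2.499 and so on). Points survived in those two rows, and the comma pattern holds in all 14 limits, so a chance misreading is unlikely. A systematic one cannot be excluded from the text alone, so the source page has to be checked.

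Second, the harm needs the printed cells/L line to be programmed literally. The cells/mm³ line stands first in each cell, runs on the same scale as the eligibility limit, and is unaffected. The other line is physiologically impossible, and the by-subject listing in SAP 7.2.1.2 would show Grade 4 throughout, so a careful programmer would probably notice. This stands: it limits the likelihood, but it does not remove the contradiction.

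Third, the CD4 row also repeats its cells/mm³ figures unchanged under cells/L, so the cells/L entries are loose in more than two rows. CD4 is not among the tests in Protocol Table 12, so this has no consequence for the analysis.

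A reader might also infer that the error drives the Grade 3 and 4 toxicity rules. The documents do not support that. Under Protocol 9.10 to 9.10.3, a bare grade does not lead to withholding or stopping: clinical significance, confirmation on repeat and relatedness also count, and a clinically nonsignificant Grade 4 laboratory value is expressly allowed to continue.

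**Conclusion.** As the table reads, the two unit lines for platelets and WBC contradict each other by a factor of 1000 in all 14 cells/L limits. This holds subject to one check of the source page for a misread decimal point.

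The effect on results is conditional. If the printed cells/L limits are applied to results in 10⁹/L, 100% of subjects with physiological counts are Grade 4 at Baseline, and 0% of those with a Baseline value can have a treatment-emergent decrease. If grading uses the cells/mm³ limits or their exact conversion, nothing changes. A reader should not conclude that the tables will in fact be wrong: the documents give neither the central laboratory's unit nor the line that the program uses. That silence is why the point should be closed before the tables are produced.

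**What to change.** 1. Check the source page of Appendix 1. If the commas are there, reconcile the two unit lines so that each cells/L entry is the conversion of the cells/mm³ entry in the same cell: platelets 100 to <125, 50 to <100, 25 to <50 and <25 × 10⁹/L; WBC 2.000 to 2.499, 1.500 to 1.999, 1.000 to 1.499 and <1.000 × 10⁹/L. This only restates the limits already printed in the other unit.
2. Add one sentence to SAP 7.2.1 saying that platelets and WBC are graded on the cells/mm³ limits or their exact conversion.
3. Before the laboratory abnormality tables are run, verify the units of the incoming results and of the limits in the grading program, for example by grading a platelet count of 250 × 10⁹/L and a WBC of 7 × 10⁹/L and confirming that neither receives a grade.

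The study was terminated in February 2023 and all active subjects have completed the 48-week treatment period (SAP 1), so steps 2 and 3 protect the analysis; correcting the appendix mainly keeps the record straight. The cost is two table rows, one sentence and a short program check, with no new data.

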## **APPENDIX 2. PREGNANCY PRECAUTIONS AND THE DEFINITION OF CHILD-BEARING POTENTIAL AND CONTRACEPTIVE REQUIREMENTS**

### **Pregnancy Precautions**

The effect of VBR and AB-729 on pregnancy has not been assessed. In preclinical studies, there was no evidence of embryo-fetal toxicity with VBR, while maternal toxicity was observed in initial dose range-finding studies with AB-729 in rats and rabbits (further studies are ongoing); refer to the respective IBs for details. Pregnancy precautions are required and contraceptive requirements for female subjects of child-bearing potential are described below.

#### Definition of Female Subjects of Child-bearing Potential

A female subject is considered of child-bearing potential unless they are in the following categories:

- Premenarchal
- Premenopausal with 1 of the following:
  - Documented hysterectomy
  - Documented bilateral salpingectomy
  - Documented bilateral oophorectomy
- Postmenopausal: A postmenopausal state is defined as age >54 years with no menses for 12 months without an alternative medical cause.

For individuals with permanent infertility due to an alternate medical cause other than the above, (eg, Müllerian agenesis, androgen insensitivity), Investigator discretion should be applied to determining study entry.

Documentation to determine child-bearing potential can come from the site personnel's review of the subject's medical records, medical examination, or medical history interview.

### **Contraceptive Requirements**

The drug-drug interaction of VBR and systemic (oral/injectable/implantable) hormonal contraceptives has not been assessed and so systemic hormonal contraceptives are not considered an effective contraceptive method for female subjects of child-bearing potential for the purposes of this study.

Female subjects of child-bearing potential (defined above) must agree to use dual effective contraceptive methods for the duration of the study and follow-up, or for at least 28 days after the last dose of VBR (Group 2 in [Figure 6](#)) and 6 months after the last dose of AB-729 (Groups 1 and 3 in [Figure 6](#)) if the subject prematurely discontinues from the study.

Effective contraceptive methods include male or female condom (may not be used together due to increased risk of breakage), vasectomy, tubal sterilization, intra-uterine device (IUD), diaphragm, or cervical cap. Female subjects of childbearing potential must have a negative serum pregnancy test at Screening and a negative urine pregnancy test prior to receiving the first dose of study drug on Day 1.

All male subjects must agree to use dual effective contraceptive methods with their female partners (if their female partner is of child-bearing potential) for the duration of the study and follow-up, or for at least 28 days after the last dose of VBR (Group 2 in [Figure 6](#)) and for 6 months after the last dose of AB-729 (Groups 1 and 3 in [Figure 6](#)) if they prematurely discontinue the study. In this case, effective contraceptive methods may include systemic (oral/injectable/implantable) hormonal contraceptives, vasectomy, tubal sterilization, IUD, diaphragm, or cervical cap. Male subjects must avoid sperm donation from the time of the first dose of study drug and throughout the study period or for at least 28 days after the last dose of VBR (Group 2 in [Figure 6](#)) and for 6 months after the last dose of AB-729 (Groups 1 and 3 in [Figure 6](#)) if they prematurely discontinue the study.

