## 7 DISCONTINUATION OF STUDY TREATMENT AND SUBJECT DISCONTINUATION/WITHDRAWAL

### 7.1 Discontinuation of Study Treatment

With the exception of treatment cessation based on Treatment Stopping Criteria (see [Section 4.1.1](#)), if an individual subject is not satisfactorily tolerating their assigned treatment due to any AEs in the judgment of the Investigator, then, upon consultation with the Sponsor, the Investigator may discontinue treatment with VBR and/or AB-729 depending on the treatment group assignment. Discontinuation from treatment does not mean discontinuation from the study. Subjects who prematurely discontinue their assigned treatment regimen should immediately undergo the assessments listed for the Premature Termination visit ([Section 8.5](#)) and then continue scheduled follow-up assessments ([Table 11](#)).

- If both or either IMP is discontinued, the subject may remain on NrtI as clinically indicated at the discretion of the Investigator.
- For subjects in Group 1, if the NrtI is discontinued, then VBR must also be discontinued; treatment with AB-729 may be continued following discussion with the Medical Monitor. In this event, subjects will not be required to undergo a premature termination visit, and will continue with their scheduled visits, as planned.

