HCV Ab, HDV Ab, HIV Ab, HAV Ab, HEV Ab	X																
Confirm subject eligibility	X	X															
Randomization		X															
Dispense VBR		X		X	X	X	X	X	X	X	X	X	X	X			
VBR administration (Groups 1, 2)		X	X	X	X	X	X	X	X	X	X	X	X	X	X		
NrtI administration (All subjects)		X	X	X	X	X	X	X	X	X	X	X	X	X	X		
AB-729 administration (Group 1, 3)		X			X		X		X		X		X				
VBR accountability			X	X	X	X	X	X	X	X	X	X	X	X	X	X	X
Review subject dosing diary			X	X	X	X	X	X	X	X	X	X	X	X	X	X	X
Review injection site reaction diary (Groups 1 and 3)			X			X		X		X		X		X		X	
Sparse PK of VBR (Groups 1, 2)		X	X	X	X	X	X	X	X	X	X	X	X	X	X	X	X
Sparse PK of NrtI (All subjects)		X	X	X	X	X	X	X	X	X	X	X	X	X	X	X	X
Sparse PK of AB-729 (Group 1, 3) j		X j			X		X		X		X		X j				
Optional intensive PK substudy of AB-729		X k											X k				
Optional pharmacogenomic sample							X l										

Vebicorvir

ABI-H0731-204 Protocol Amendment 1 27 October 2021

Period or Visit	Screen	On Treatment														PT a	UV b
Study Day or Week	D-45 to D-1	D 1	Wk 2	Wk 4	Wk 8	Wk 12	Wk 16	Wk 20	Wk 24	Wk 28	Wk 32	Wk 36	Wk 40	Wk 44	Wk 48	NA	NA
Visit Windows (days)	NA	0	±3	±3	±3	±3	±3	±3	±3	±3	±3	±3	±3	±3	±3	NA	NA
Assessment of Treatment Stopping Criteria (see Section 4.1.1 )															X m		

Abbreviations: Ab=antibody; AE=adverse event; AFP=alpha fetoprotein; APRI=aspartate aminotransferase to platelet ratio index; CrCl=creatinine clearance; D=day; DNA=deoxyribonucleic acid; ECG=electrocardiogram; HbA1c=glycated hemoglobin; HBcrAg=hepatitis B core-related antigen; HBeAb=anti-hepatitis B e antigen antibody; HBeAg=hepatitis B e antigen; HBsAb=anti-hepatitis B surface antigen antibody; HBsAg=hepatitis B surface antigen; HBV=hepatitis B virus; HCV=hepatitis C virus; HDV=hepatitis D virus; HEV=hepatitis E virus; HIV=human immunodeficiency virus; IRT= Interactive Response Technology; NA=not applicable; NrtI=nucleos(t)ide/reverse transcriptase inhibitor; PK=pharmacokinetic(s); PT=Premature Termination visit; RNA=ribonucleic acid; TNA=total nucleic acids; UV=Unscheduled visit; Wk(s)=week(s); VBR=vebicorvir.

- a Subjects who prematurely discontinue their assigned treatment regimen before the Week 48 visit should immediately undergo the assessments listed for the Premature Termination visit and then continue with Weeks 52 to 96 follow-up assessments (see [Table 11](#)).

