**Table 11. Schedule of Assessments (Cohort 1) – Follow-up for Rest of the Subjects**

Study Day or Week	Wk 52	Wk 56	Wk 60	Wk 64	Wk 68	Wk 72	Wk 76	Wk 80	Wk 84	Wk 88	Wk 92	Wk 96
Visit Windows (days)	±5	±5	±5	±5	±5	±5	±5	±5	±5	±5	±5	±5
Weight						X						X
Vital signs	X	X	X	X	X	X	X	X	X	X	X	X
Complete physical exam						X						X
Symptom-directed physical exam	X	X	X	X	X		X	X	X	X	X	
12-lead ECG a			X									X
Review of concomitant medications & AEs	X	X	X	X	X	X	X	X	X	X	X	X
Fibroscan ® (if available)						X						X
FibroTest ® , APRI						X						X
Chemistry, hematology, coagulation	X	X	X	X	X	X	X	X	X	X	X	X
CrCl						X						X
Pregnancy test b	X	X	X	X	X	X	X	X	X	X	X	X
Urinalysis	X	X	X	X	X	X	X	X	X	X	X	X
HBV DNA (COBAS ® TaqMan ® )			X			X			X			X

Vebicorvir

ABI-H0731-204 Protocol Amendment 1 27 October 2021

Study Day or Week	Wk 52	Wk 56	Wk 60	Wk 64	Wk 68	Wk 72	Wk 76	Wk 80	Wk 84	Wk 88	Wk 92	Wk 96
Visit Windows (days)	±5	±5	±5	±5	±5	±5	±5	±5	±5	±5	±5	±5
HBV RNA (COBAS®)	X	X	X	X	X	X	X	X	X	X	X	X
HBV TNA	X	X	X	X	X	X	X	X	X	X	X	X
Qualitative HBeAg			X			X			X			X
HBeAb			X			X			X			X
Quantitative HBsAg c	X	X	X	X	X	X	X	X	X	X	X	X
HBcrAg			X			X			X			X
HBsAg isoforms	X	X	X	X	X	X	X	X	X	X	X	X
Immune complexes	X	X	X	X		X			X			X
Sample for HBV resistance monitoring	X	X	X	X	X	X	X	X	X	X	X	X
Virology back-up sample d	X	X	X	X	X	X	X	X	X	X	X	X
Immune biomarkers/cytokines		X		X		X			X			X
PBMCs e		X		X		X			X			X
RNAi biomarker sample	X	X	X	X	X	X	X	X	X	X	X	X
NrtI administration (see Sections 4.1.1, 4.1.2)	X	X	X	X	X	X	X	X	X	X	X	X
Review subject dosing diary	X	X	X	X	X	X	X	X	X	X	X	X
Sparse PK of VBR (Groups 1, 2)	X											
VBR accountability (Groups 1, 2) f	X											

Abbreviations: Ab=antibody; AE=adverse event; APRI=aspartate aminotransferase to platelet ratio index; CrCl=creatinine clearance; DNA=deoxyribonucleic acid; ECG=electrocardiogram; HBcrAg=hepatitis B core-related antigen; HBeAb=anti-hepatitis B e antigen antibody; HBeAg=hepatitis B e antigen; HBsAg=hepatitis B surface antigen; NrtI=nucleos(t)ide/reverse transcriptase inhibitor; PK=pharmacokinetic(s); RNA=ribonucleic acid; TNA=total nucleic acids; UV=Unscheduled visit; Wk(s)=week(s); VBR=vebicorvir.

a Any clinically significant ECG result will be confirmed.

b Pregnancy tests may be conducted by urine dipstick. If positive on dipstick, reflex to serum.

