### **8.3.5 Week 52 Through Week 96 Follow-Up Visits for Rest of the Subjects (±5 Days)**

The following follow-up assessments will be performed every 4 weeks from Study Weeks 52 through 96, for subjects who do NOT meet the Treatment Stopping Criteria, or subjects who meet the NrtI-restart criteria after having met Treatment Stopping Criteria, or subjects who prematurely discontinue treatment with VBR/AB-729 at any time (see [Table 11](#)):

- NrtI and VBR will continue to be administered at home until laboratory results from the Week 48 visits are available to adjudicate the individual subject Treatment Stopping Criteria (see [Section 4.1.1](#)). Once a subject is determined to not meet the Treatment Stopping Criteria, he/she will be notified by the site, and the subject will discontinue treatment with VBR.
- NrtI administration once daily at home through Week 96
- Measure body weight (Weeks 72 and 96 only)
- Record vital signs (temperature, heart rate, respiration rate, and blood pressure)
- Complete physical examination (excluding breast and genitalia, unless indicated; Week 72 and 96 only); all other visits, symptom-directed physical examination
- 12-lead ECG (Weeks 60 and 96 only)
- Review AEs and concomitant medications
- FibroScan (if available; Weeks 72 and 96 only)
- Obtain blood samples for the following:
  - Safety laboratory tests:
    - chemistry, hematology, coagulation
    - CrCl (Weeks 72 and 96 only)
  - Virology:
    - HBV TNA, HBV RNA
    - HBV DNA (Weeks 60, 72, 84, and 96 only)
    - HBsAg, HBsAb (only if HBsAg <LLOQ), HBsAg isoforms, HBV resistance monitoring sample
    - Immune complexes (Weeks 52, 56, 60, 64, 72, 84, and 96 only)
    - HBeAg, HBeAb, HBcrAg (Weeks 60, 72, 84, and 96 only)
    - Virology back-up sample (to be used for retesting HBV parameters)
  - Other:
    - FibroTest, APRI (both at Week 72 and 96 only)

- A single off-treatment blood sample for sparse PK of VBR (Groups 1 and 2; Week 52 only)
- Cytokines/Immune biomarkers (Weeks 56, 64, 72, 84, and 96 only)
- PBMCs (at selected sites at Weeks 56, 64, 72, 84, and 96; not to be collected at subsequent timepoints if not collected at Day 1)
- RNAi biomarker
- Obtain urine samples for the following:
  - Pregnancy test for female subjects of child-bearing potential
  - Urinalysis
- Subject dosing diary
- VBR accountability (Groups 1 and 2; Week 52 only)

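### Appendix 2 gives the 28-day post-VBR contraception and sperm-donation period to Group 2 only, although Group 1 also takes VBR; the gap is real but very narrow

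*Combined protocol and SAP*

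**What the plan says.** Appendix 2 (Contraceptive Requirements) sets three rules: contraception for women of child-bearing potential, contraception for men, and sperm donation. For contraception, the basic duty runs "for the duration of the study and follow-up"; the sperm-donation rule likewise runs through the study period. The day counts matter only for someone who leaves the study prematurely. For those subjects each rule names two periods by group:

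- after VBR: "for at least 28 days after the last dose of VBR (Group 2 in" Figure 6);
- after AB-729: "6 months after the last dose of AB-729 (Groups 1 and 3 in" Figure 6).

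Group 1 receives VBR, AB-729 and NrtI (protocol Table 7), and Table 9 has a row for "VBR administration (Groups 1, 2"). Inclusion criterion 11 requires agreement to Appendix 2, so this is the operative text.

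Protocol Section 6.3.1 also has a 28-day window after VBR, labelled Groups 1 and 2. It deals only with whether systemic hormonal methods count as acceptable for women. It sets no general contraception period, and nothing for men.

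**The concern.** Read literally, a Group 1 subject who leaves early has no contraception or sperm-donation period counted from the last VBR dose. The 6 months after AB-729 stand in for it, which works only while VBR does not outlast AB-729 by too much. If AB-729 ends early and VBR continues, a Group 1 subject could leave with fewer than 28 days required after VBR, or none, while a Group 2 subject with the same VBR exposure has 28.

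The protocol does not exclude that sequence. Section 7.1 says "the Investigator may discontinue treatment with VBR and/or AB-729 depending on the treatment group assignment", and adds that "Discontinuation from treatment does not mean discontinuation from the study". AB-729 is given in the clinic (6.1.3), missed doses are foreseen (6.1.2.4), study drug may be couriered to the home (8.2), and study drug is withheld for a related, confirmed Grade 3 event (9.10.2). The SAP tabulates completion and AE-related discontinuation separately for each drug (4.1, 7.1.6).

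Leaving on the day VBR stops also became an instruction for some. SAP 1.2 has subjects who reached Week 48 after the February 2023 termination stop VBR and move to care outside the study at the same visit.

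**Working it through.** The plan gives no figure to reproduce, so this is date arithmetic.

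**Inputs**
- AB-729 doses: Day 1 and Weeks 8, 16, 24, 32, 40 (Table 9, Section 8.3.3).
- VBR stop: Week 48, or later while Week 48 results are awaited (Section 4.3). I take Weeks 48 to 52, since VBR accountability is done at Week 50 or 52 (Tables 10 and 11).
- VBR need: 28 days, or 4 weeks.
- AB-729 period: 6 months. Assumed to be 26 weeks; calendar range 181 to 184 days.

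**Formulas, in weeks**
- Cover ends at max(study exit, last AB-729 dose + 26, VBR stop).
- Need ends at VBR stop + 4.
- Uncovered = max(0, VBR stop + 4 − cover end).

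**Planned schedule.** Cover ends at 40 + 26 = Week 66. Need ends at 48 + 4 = Week 52 to 52 + 4 = Week 56. Cover exceeds need by 66 − 56 = 10 to 66 − 52 = 14 weeks.

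**Threshold.** A gap needs (VBR stop − last AB-729 dose) above 6 months − 28 days. That is 181 − 28 = 153 to 184 − 28 = 156 days, or 21.9 to 22.3 weeks. It also needs exit within 28 days of the last VBR dose, because a subject still in the study is covered.

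**Uncovered weeks for a Group 1 early leaver**

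| Last AB-729 dose | Doses not given | VBR must run past Week | VBR to 48, exit 48 | VBR to 48, exit 50 | VBR to 48, exit 52 | VBR to 50 or 52, exit same day |
|---|---|---|---|---|---|---|
| Day 1 | 5 | 22 | 4 | 2 | 0 | 4 |
| Week 8 | 4 | 30 | 4 | 2 | 0 | 4 |
| Week 16 | 3 | 38 | 4 | 2 | 0 | 4 |
| Week 24 | 2 | 46 | 2 | 2 | 0 | 4 |
| Week 32 | 1 | 54 | 0 | 0 | 0 | 0 |
| Week 40 | 0 | 62 | 0 | 0 | 0 | 0 |

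**Week 24 / Week 48 case in days, exit at Week 48.** VBR stops (48 − 24) × 7 = 168 days after the last AB-729 dose. Remaining AB-729 cover is 181 − 168 = 13 to 184 − 168 = 16 days. Uncovered: 28 − 13 = 15 down to 28 − 16 = 12 days. The first 2 weeks after VBR are essentially covered.

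**Week 32 at the edges of the visit windows.** Last AB-729 at Week 32 − 3 days (day 221) and VBR to Week 52 + 5 days (day 369) gives 369 − 221 = 148 days, below 153. There is no gap.

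With VBR to Week 48, a shortfall therefore needs at least the last two of the six AB-729 doses not given. If 6 months were read as 24 weeks (168 days), the threshold would be 20 weeks instead of about 22.

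**The case against.** The strongest reply is that the label is deliberate. Appendix 2 gives each group its controlling period, and for Group 1 that is the longer AB-729 one. Section 6.3.1 does the mirror image: its AB-729 clause names Group 3 only, although Group 1 also receives AB-729. This is a fair reading and it holds on the planned schedule. It fails only where VBR outlasts AB-729 by more than about 22 weeks.

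The second reply is that the protocol does not schedule such a sequence. Section 8.3.5 puts "subjects who prematurely discontinue treatment with VBR/AB-729 at any time" on the Table 11 visits. Table 11 has a row for "NrtI administration (see Sections 4.1.1, 4.1.2") and none for giving VBR. The one arrangement in Section 7.1 that explicitly keeps a Group 1 subject on scheduled visits with a single investigational drug runs the other way: VBR stops and AB-729 may continue. This stands for formal discontinuation and makes the route unlikely. Missed or withheld AB-729 doses do not by themselves trigger that move. How far they could accumulate depends on the Pharmacy Manual, which is not available here. Section 9.10.2 speaks only of withholding study drug, which SAP 3.6.1 defines as both drugs, so it does not settle whether VBR would continue alone.

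Third, the consequence is slight, and that stands in full. Section 7.3 expects withdrawal to be uncommon. Appendix 2 reports no embryo-fetal toxicity with VBR in preclinical studies, though it also says the effect on pregnancy has not been assessed. The amendment rationale in Appendix 3 regards 2 weeks as long enough for VBR clearance. The SAP termination instruction shows the timing of exit, not that anyone's AB-729 had ended by Week 24.

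**Conclusion.** The point holds as an incomplete group label with a very small consequence. No text sets a general post-VBR contraception or sperm-donation period for Group 1, and the AB-729 period fills in for it except when all three conditions coincide: last AB-729 dose at about Week 24 or earlier, VBR more than about 22 weeks beyond it, and exit within 28 days of the last VBR dose. The shortfall is then up to 28 days. It is zero for anyone dosed with AB-729 at Week 32 or later.

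This rests on 6 months being 181 to 184 days, on VBR ending at Weeks 48 to 52, and on the protocol not ruling out continued VBR after missed, withheld or stopped AB-729. The cases are scenarios, not frequencies. Section 6.3.1 does not contradict Appendix 2; it covers a different question. A remoter case is a Group 1 subject who took VBR but never received AB-729, who would have no post-dose period at all; this is unlikely because both drugs are given in clinic on Day 1. With dosing finished, the main value of the correction is wherever this wording is reused.

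**What to change.** In the three Appendix 2 sentences (female contraception, male contraception, sperm donation), change the label on the VBR period from Group 2 to Groups 1 and 2. Add one clause: for Group 1, the later of the two end dates applies, 28 days after the last VBR dose or 6 months after the last AB-729 dose. Leave Section 6.3.1 as it is.

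With this change cover always reaches at least VBR stop + 4 weeks, so the shortfall is zero for every combination of stop dates. The cost is three labels and one clause. There is no new procedure, and nothing changes for subjects on the full schedule.
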